9.4. Pharmacodynamic Analyses

Pharmacodynamic analysis will use Pharmacodynamic Analysis Set and will be analyzed based on randomized treatment group.

9.4.1. Analyses of Anthropomorphic Measurements

The observed values and the change from baseline and percent change from baseline for body weight, BMI, [REDACTED] will be presented by visit and treatment group.

MMRM analysis will be used to analyze the change from baseline and percent change from baseline in anthropomorphic measurements.

Line plots (\pm SE) of the change from baseline LS mean over time may be presented by treatment group.

9.4.2. Analyses of Laboratory Parameters

9.4.2.1. Lipids

The observed values and the change from baseline and percent change from baseline for triglycerides, non-HDL cholesterol, HDL-c, LDL-c, [REDACTED] will be presented by visit and treatment group. Only records where fasting is confirmed will be used for summary and analysis.

The following categories will be included in the descriptive summary by visit:

- Triglycerides <150, 150-<200, \geq 200 mg/dL
- LDL-c <130 and \geq 130 mg/dL

MMRM analysis will be used to analyze the change from baseline and percent change from baseline in lipids.

Non-parametric analysis of the change from baseline and percent change from baseline by visit for triglycerides will be compared by treatment group and the p-value from the Wilcoxon Rank Sum test will be presented. The Hodges-Lehmann estimate of location shift will be used to estimate the median and the exact 90% confidence limits.

Line plots (\pm SE) of the change from baseline LS mean over time may be presented by treatment group.

In addition, waterfall plots for the individual percent change from baseline to Day 50, change from baseline to Day 50, percent change from baseline to Day 92, change from baseline to Day 92 will be generated.

9.4.2.2. Metabolic Biomarkers

The observed values and the change from baseline and percent change from baseline for [REDACTED], Adiponectin, HbA1c, HOMA-IR, FFA, Adipo-IR (fasting FFA * fasting insulin), [REDACTED], fasting glucose and fasting insulin (not from OGTT) will be presented by visit and treatment group.

HOMA-IR value is calculated by multiplying fasting Glucose (mg/dL) with fasting Insulin (uIU/ml) and then dividing by 405.

HOMA-IR value (SI units) is calculated by multiplying fasting Glucose (mmol/L) with fasting Insulin (uIU/ml) and then dividing by 22.5.

MMRM analysis will be used to analyze the change from baseline in metabolic biomarkers.

9.4.2.3. Liver Biomarkers

The observed values and the change from baseline for ALT, AST, [REDACTED] (derived from hyaluronic acid [HA], amino-terminal propeptide of type III procollagen [PIINP], tissue inhibitor of metalloproteinase 1 [TIMP-1]), INR, Pro-C3, total bilirubin (TB), direct bilirubin, [REDACTED] will be presented by visit and treatment group.

A listing of only abnormal liver biomarker records will be provided.

MMRM analysis will be used to analyze the change from baseline in liver biomarkers.

Line plots (\pm SE) of the change from baseline LS mean over time may be presented by treatment group.

9.4.3. Analyses of MRI Measures

The observed values and the change from baseline and percent change from baseline in MRI-PDFF, [REDACTED] will be presented by visit and treatment group.

The following criteria will also be summarized at Day 50 and Day 92 based on observed data at that visit:

- Percentage reduction from baseline MRI-PDFF $\geq 30\%$ and $< 30\%$
- MRI-PDFF $\geq 5\%$ or $< 5\%$

MMRM analysis will be used to analyze the change from baseline and percent change from baseline in MRI-PDFF, abdominal visceral fat, abdominal subcutaneous fat, liver volume.

In addition, a bar chart of LS mean (\pm SE) percent change from baseline to Day 50, change from baseline to Day 50, percent change from baseline to Day 92, change from baseline to Day 92 in MRI-PDFF by treatment group.

9.4.3.1. Responder Analysis

Responder analysis will be performed for MRI-PDFF. The proportion of subjects that reach a percentage reduction of ≥ 10 , ≥ 20 , ≥ 30 , ≥ 40 and ≥ 50 in MRI-PDFF will be summarized based on observed data at that visit. The following will be analyzed with a Fisher's Exact Test.

- Proportion of subjects who have ≥ 30 percent reduction in MRI-PDFF from baseline to Day 92.

- Proportion of subjects who have ≥ 30 percent reduction in MRI-PDFF from baseline to Day 50.
- Proportion of subjects who have MRI-PDFF $< 5\%$ at Day 92.
- Proportion of subjects who have MRI-PDFF $< 5\%$ at Day 50.

9.4.3.2. **Supportive Analysis**

Supportive analysis of MRI-PDFF will be performed: with sensitivity analysis to assess impact of missing data using multiple imputation using a pattern-mixture model (PMM) approach using control-based pattern imputation, correlation analysis and non-parametric analysis.

9.4.3.2.1. **Multiple Imputation Using Control Based Pattern-Mixture Model**

Multiple imputation will be performed using the placebo group to impute the missing values for the BIO89-100 subjects. This imputation will account for the possibility that not all data are missing at random. This method of multiple imputation assumes that the missing data post study discontinuation for BIO89-100 subjects are missing not at random (MNAR). By using the placebo subject data to impute the missing data from the BIO89-100 group, the analysis will produce a conservative estimate of the treatment effect of BIO89-100, although not as conservative as the worst observed case analysis.

Prior to applying the control-based pattern mixture, the first step will be to impute the non-monotone missing data assuming the missing at random (MAR) assumption. Only missing data that are sandwiched by two non-missing records in time will be imputed using the MAR assumption. Visit window mapping should also decrease the amount of non-monotone missing imputations that need to be done. After the non-monotone missing data patterns are filled in then the control-based imputation is applied.

| Missing Data Pattern | Baseline | D50 | D92 |
|----------------------|----------|-----|-----|
| Monotone | X | X | .b |
| Non-Monotone | X | .a | X |

.a is a missing value that will be imputed assuming the MAR assumption because it is sandwiched by two non-missing records; the earlier records will be imputed first.

.b is a missing value that will be imputed assuming the NMAR assumption because it is monotone missing.

9.4.3.3. **Correlation Analysis**

Correlation analysis will be performed for MRI-PDFF and key liver biomarker data using the PD analysis set. The pairwise Pearson correlation will be calculated for each combination of MRI-PDFF, CAP score, VCTE score, ALT, AST, ELF Score, Pro-C3, triglycerides, LDL and HDL change from baseline within Day 50, within Day 92 and between Day 50 and Day 92 by treatment group (subjects on BIO89-100 only) and for pooled placebo.

9.4.3.4. **Non-Parametric Analysis**

Non-parametric analysis of the change from baseline and percent change from baseline to Day 50 and Day 92 for MRI-PDFF will be compared by treatment group and the p-value from the

Wilcoxon Rank Sum test will be presented. The Hodges-Lehmann estimate of location shift will be used to estimate the median and the exact 90% confidence limits.

9.5. Safety Analyses

Safety analysis will use the Safety Analysis Set and will be analyzed based on actual treatment group.

9.5.1. Adverse Events

All adverse events will be coded using the MedDRA (version 23.0 – Apr 2020).

The incidence and number of events of the following will be summarized by treatment and overall:

- Overall TEAE Summary*
- TEAEs by System Organ Class (SOC) and Preferred Term (PT)
- Serious TEAEs by SOC and PT
- Serious Related TEAEs by SOC and PT
- Serious TEAEs Leading to Study Discontinuation by SOC and PT
- Serious TEAEs Leading to Investigational Product Discontinuation by SOC and PT
- Related TEAEs by SOC and PT
- TEAEs Leading to Study Discontinuation by SOC and PT
- Fatal TEAE (will be provided in a listing)
- TEAEs by SOC, PT and Maximum CTCAE Grade
- TEAEs by SOC, PT and CTCAE Grade
- TEAEs Leading to Investigational Product Discontinuation by SOC and PT
- TEAEs by PT in Descending Frequency
- TEAE by SOC and PT in subgroup of Biopsy confirmed NASH (Yes if F1, F2, F3, else No) Yes/No

When calculating incidence; subjects will only be counted once per SOC, PT, or grade.

When deriving relationship of AEs to study treatment, categories with the relationship of “definitely related”, “probably related”, “possibly related” will be considered “related”. If an AE has missing relationship, it will be assumed to be related to the investigational product for analysis purposes. If an AE has missing CTCAE grade, the missing grade will be imputed as a severe grade 3 adverse event. Any TEAE related to VOCID19 will be provided in a listing.

TEAEs by System Organ Class (SOC) and Preferred Term (PT) by subgroup of biopsy confirmed NASH (Yes if F1, F2, F3, else No) will be summarized.

*In the Overall TEAE summary, the most severe CTCAE grade will be summarized for each subject.

9.5.2. Clinical Laboratory Evaluations

The observed values and the change from baseline for labs (biochemistry, hematology, urinalysis) will be summarized by visit and treatment group. Pharmacodynamic endpoints summarized via MMRM will not be presented in the safety lab change from baseline tables.

A listing of only abnormal labs (biochemistry, hematology, urinalysis) will be provided.

Shift tables will use the reference range result of low, normal, high to summarize lab (biochemistry and hematology) or normal and abnormal for select urinalysis shifts from baseline to each post-baseline visit. All labs with a reference range result will be included in shift tables. The percentage of the shifts will be derived using the number of subjects at the baseline range level as the denominator. Pharmacodynamic endpoints summarized via MMRM will be presented in the safety lab shift tables.

The observed value and the change from baseline in cortisol will be summarized descriptively in the urinalysis tables.

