7.2.5. Clinical Safety Laboratory Assessments

See Appendix 2 (Section 9.2) for the list of clinical laboratory tests to be performed and the SoAs (Table 2 for Cohorts 1-4, Table 4 for Cohorts 5-6, and Table 6 for Cohort 7) for the timing and frequency. Laboratory tests should be performed under fasting conditions (≥ 10 hours).

Fasting includes food and all beverages except for non-mineral water. It is recommended that subjects abstain from consumption of alcoholic beverages for at least 24 hours before laboratory test assessments.

The Investigator must review the laboratory report, document this review, and record any clinically relevant changes occurring during the study in the AE section of the eCRF. The laboratory reports must be filed with the source documents. Clinically significant abnormal laboratory findings are those which are not associated with the underlying disease, unless judged by the Investigator to be more severe than expected for the subject's condition.

All laboratory tests with values considered clinically significantly abnormal during participation in the study or within 28 days after the last dose of study intervention should be repeated until the values return to normal or baseline or are no longer considered clinically significant by the Investigator or Sponsor's Medical Monitor.

If such values do not return to normal/baseline within a period of time judged reasonable by the Investigator, the etiology should be identified and the Sponsor notified.

All protocol-required laboratory assessments, as defined in Appendix 2 (Section 9.2), must be conducted in accordance with the relevant study manual and the SoAs (Table 2 for Cohorts 1-4, Table 4 for Cohorts 5-6, and Table 6 for Cohort 7).

If laboratory values from non-protocol specified laboratory assessments performed at the institution's local laboratory require a change in subject management or are considered clinically significant by the Investigator (e.g., SAE or AE or skipping of dose), then the results must be recorded in the eCRF and the Sponsor should be notified.

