4.3. Other Safety Endpoints

The other safety endpoints are:

- Change from baseline in vital signs
- Incidence and shifts of clinically significant vital signs
- Incidence of clinically significant physical examination findings
- Incidence and shifts of clinically significant electrocardiograms (ECG)
- Incidence and shifts of clinically significant laboratory abnormalities
- Change from baseline in safety laboratory evaluations including complete blood count (CBC), blood biochemistry, cortisol and urinalysis over time

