9.1.3. Analysis Visits and Visit Windowing

In general, all scheduled visits will be used as analysis visit for descriptive analysis tables and listings.

If a scheduled visit is missing, an unscheduled visit may be mapped to take its place if and only if it is within the visit window of the missing scheduled visit. The following table describes the visit mapping of unscheduled post-baseline visits in the event that a scheduled visit is missing. If there are multiple unscheduled visits, the closest one to the projected date will be selected; if there are ties, the later measurement will be used.

| Parameter | Analysis Visit/Time Point Window |
|--------------------------|---|
| Labs | Study Day \pm 3 days from Target Day ET visits are mapped to the nearest missing analysis visit, using the same window, after unscheduled visits are considered. |
| MRI; Fibroscan | Day 50: $36 \leq$ Study Day ≤ 64 (± 14 Days); Day 92: Study Day ≥ 78 ; ET visits within Study Day < 65 will be mapped to Day 50; ET visits with Study Day ≥ 65 will be mapped to Day 92. |
| Vital Signs | Study Day \pm 3 days from Target Day; ET visits are mapped to the nearest missing analysis visit, using the same window, after unscheduled visits are considered. |
| Anthropomorphic Measures | Study Day \pm 3 days from Target Day (For body weight) Study Day \pm 14 days from Target Day (For waist-hip ratio related parameters) ET visits are mapped to the nearest missing analysis visit, using the same window, after unscheduled visits are considered |
| ECG | Study Day \pm 3 days from Target Day ; ET visits are mapped to the nearest missing analysis visit after unscheduled visits are considered using Study Day |
| PK | Depending on the time point, the window for each time point is specified in the PK sampling schedule. If multiple unscheduled records are available, the sample collected closest to the nominal time will be selected. If the distance is the same, the later one will be selected. (Actual time should be used for PK analysis) |

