9.5.4. Vital Signs

The observed values and the change from baseline for vital signs will be summarized by visit and treatment group. On visits where multiple ECGs are taken, only pre-dose will be summarized.

The number of subjects meeting the following criteria will be summarized considering all post-baseline visits including unscheduled:

- Absolute value of SBP < 90 mm Hg
- Absolute value of DBP < 50 mm Hg
- Pulse rate < 50 bpm
- Pulse rate > 120 bpm
- Maximum increase from baseline in SBP \geq 30 mm Hg
- Maximum increase from baseline in DBP \geq 20 mm Hg

- Maximum decrease from baseline in SBP ≥ 30 mm Hg
- Maximum decrease from baseline in DBP ≥ 20 mm Hg

Shift tables will be used to summarize clinically significant shifts from baseline to each post baseline visit in the following criteria:

- SBP and DBP:

| Blood Pressure Category | Systolic mm Hg | | Diastolic mm Hg |
|-------------------------|----------------|--------|-----------------|
| Hypotension | <90 | Or | <60 |
| Normal | <120 | And | <80 |
| Elevated | 120-129 | And | <80 |
| Hypertension Stage 1 | 130-139 | Or | 80-89 |
| Hypertension Stage 2 | ≥ 140 | Or | ≥ 90 |
| Crisis | >180 | And/or | >120 |

- HR (bpm): <50; 50-89; 90-99, ≥ 100

9.5.5. 12-Lead Electrocardiograms

The observed values and the change from baseline for 12-lead ECGs parameters will be summarized by visit and treatment group. Only visits where ECGs were taken pre-dose will be summarized.

For corrected QT interval by Fridericia (QTcF), the number and percentage of subjects that have a change from baseline in QTcF >30 to 60msec and >60 msec over the entire study considering all visits including unscheduled will be summarized.

Overall interpretation (Normal, Abnormal Not Clinically Significant and Abnormal Clinically Significant) will also be summarized.

The eCRF and central reader data will be listed in addition to a variable identifying if there is agreement between the PI and central reader (Y/N).

A shift table will be used to present the shifts from baseline to each visit using the following criteria:

- QTcF <450msec
- QTcF 450-480msec
- QTcF 481-500msec
- QTcF >500 msec
- Not Done/Missing

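### Outside the liver-injury thresholds, Part 1 laboratory abnormalities are tabulated only visit by visit, so no laboratory table gives the number of subjects ever abnormal

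*SAP*

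**What the plan says.** Part 1 SAP 4.3 lists among the other safety endpoints "Incidence and shifts of clinically significant laboratory abnormalities". The endpoint thus has two halves, incidence and shifts.

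Part 1 SAP 9.5.2 is where laboratory safety data are analysed. It gives observed values and changes by visit. It adds "A listing of only abnormal labs (biochemistry, hematology, urinalysis) will be provided". It specifies shift tables by reference range: low, normal and high for biochemistry and hematology, and "normal and abnormal for select urinalysis shifts from baseline to each post-baseline visit". On percentages it says: "The percentage of the shifts will be derived using the number of subjects at the baseline range level as the denominator".

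Part 1 SAP 9.1.3 decides which results reach those tables. "In general, all scheduled visits will be used as analysis visit for descriptive analysis tables and listings". For gaps in the planned data the rule is that "an unscheduled visit may be mapped to take its place if and only if it is within the visit window of the missing scheduled visit"; for laboratory tests the window is 3 days either side of the target day.

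Protocol 7.2.5 creates unscheduled results: clinically significant abnormal values "should be repeated until the values return to normal or baseline" or cease to be clinically important. Protocol Appendix 5 adds another source. After a COVID-19 interruption, hematology and biochemistry are drawn before dosing resumes even when that visit has no planned laboratory tests.

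Other sections of the same SAP treat subject-level counts differently. In 9.5.4 the number of subjects crossing vital-sign limits "will be summarized considering all post-baseline visits including unscheduled". Section 9.5.5 does the same for QTcF changes. Section 9.4.2.4 does so for the liver thresholds in subjects with normal baseline ALT or AST.

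**The concern.** A by-visit shift table answers how many subjects were out of range at a given visit. The incidence half of the endpoint asks how many subjects were ever out of range. The second cannot be recovered from the first, because the tables do not show whether the abnormal subject at one visit is the abnormal subject at the next. The SAP does promise categorical summaries by subject as well as by time point (9.1.1), but it gives no rule for reducing one subject's repeated laboratory results to a single category.

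Unscheduled results add to this. If an abnormality in hematology, creatinine, creatine kinase, glucose or electrolytes shows only at an unscheduled draw, and the neighbouring scheduled test was done, 9.1.3 keeps it out of every laboratory table.

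What is at stake is how laboratory safety is described by dose in the final report, with 6 to 14 active subjects per cohort. One subject is 1/6 = 16.7 percentage points in the smallest cohort and 1/14 = 7.1 points in the largest, if all subjects share a baseline category.

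**Working it through.** The plan states no figure for this point, so there is nothing to reproduce. The check sets the planned outputs beside the endpoint.

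**1. Which outputs serve which half of the endpoint (Part 1 SAP).**

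| Output | Counts each subject once over the study? | Uses unscheduled results? |
|---|---|---|
| 9.5.2 values and changes by visit | No | Only in place of a missing scheduled result |
| 9.5.2 shift tables | No, one shift per visit | Only in place of a missing scheduled result |
| 9.5.2 listing of abnormal results | Not a count | Not excluded |
| 9.4.2.4 liver thresholds, normal baseline | Yes | Yes |
| 9.4.2.4 liver thresholds, raised baseline | Proportion of subjects | Rule not restated |
| 9.5.1 TEAE tables | Yes, per SOC, PT or grade | Not tied to visits |
| 9.5.4 vital-sign limits | Yes | Yes |
| 9.5.5 QTcF changes | Yes | Yes |

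Vital signs and QTcF have two layers: by-visit shifts and a subject-level count over all visits. Laboratory parameters outside the liver thresholds have only the first layer.

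**2. Which unscheduled results are lost from the tables.** There are three cases.
- The scheduled value is abnormal and a repeat follows. The subject already appears as low, high or abnormal at the scheduled visit. A more extreme repeat usually falls in the same category, so the shift count does not change.
- The scheduled value is missing and an unscheduled one lies within 3 days. It is mapped and tabulated.
- The scheduled value was taken and is normal, or no laboratory test was planned near that date, and an unscheduled draw is abnormal. This result appears in no laboratory shift table.

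Only the third case removes an abnormal subject from the tables. The documents give no rate for it.

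**3. What by-visit tables can say about incidence.** Let n subjects be normal at baseline, and let k_v be the number abnormal at visit v. From the by-visit tables alone, the number ever abnormal lies between max(k_v) and the smaller of n and the sum of the k_v.

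Illustration with assumed counts: n = 14, all normal at baseline, and k_v = 1 at each of five visits.
- Lower limit: max(k_v)/n = 1/14 = 7.1% (the same subject each time).
- Upper limit: (1 + 1 + 1 + 1 + 1)/14 = 5/14 = 35.7% (five different subjects).

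Each by-visit table reads 1/14 in both cases. The 14 is right only under the stated assumption, because 9.5.2 takes as denominator the subjects in the given baseline category, not the cohort.

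**The case against.** The strongest reply is that the endpoint concerns clinically significant abnormalities, which the protocol treats as an investigator judgement. Clinically relevant changes go into the AE section of the eCRF (protocol 7.2.5) and meet the AE definition (protocol 9.3.1). The TEAE tables of SAP 9.5.1 then count each subject once per term, whichever draw revealed the event. This stands: a reader might infer that the incidence is not produced at all, and that would be wrong. What remains is that the SAP does not say the TEAE tables deliver this endpoint, and that they rest on judgement rather than on the measured values.

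A reader might also infer that peak values vanish and that laboratory toxicity is understated. The documents do not support this. A repeat prompted by an abnormal scheduled value usually leaves the category unchanged, the 24-hour post-dose tests are scheduled assessments, ET visits are summarized descriptively, and unscheduled results are not excluded from the abnormal listing. The by-visit proportions are correct for what they are.

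Nor do dose-escalation decisions hang on these tables, since the SMC reviews blinded laboratory data as the study runs.

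Two comparisons need care. The Part 2 SAP (8.1) has a general rule that worst-value summaries use all visits, but its own laboratory section (8.5.2) also specifies only by-visit shifts, so it is no model for a laboratory table. Protocol 8.4.1 plans CTCAE grading of laboratory data and comparison with prespecified boundaries, neither of which appears in Part 1 SAP 9.5.2. It would be tempting to call that an undeclared departure, because SAP section 10 declares no changes. However, the Part 1 SAP is written to protocol Version 3.0, which is not among the documents, so this cannot be established.

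**Conclusion.** The point holds in a limited form. Outside the liver thresholds of 9.4.2.4, the incidence half of the endpoint in 4.3 has no laboratory-based table, and an abnormality found only at an unmapped unscheduled draw is listed but not tabulated. Investigator-judged events are counted through the TEAE tables.

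The size cannot be fixed from the documents. The range of 7.1% to 35.7% is an illustration: it assumes 14 subjects all normal at baseline and one abnormal at each of five visits. It shows only that by-visit shifts do not determine incidence.

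The conclusion also assumes that no redacted or removed SAP text supplies such a table. This is a worthwhile and inexpensive improvement to the reporting. It does not point to an error in any planned estimate.

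**What to change.** In Part 1 SAP 9.5.2 add, for each laboratory parameter, a subject-level shift from baseline to the lowest and to the highest post-baseline value. A shift to the worst CTCAE grade would serve as an alternative, since protocol 8.4.1 already plans to present laboratory data by grade. Specify that:
- each subject is counted once per parameter and direction;
- all post-baseline results are used, including unscheduled and early termination results;
- the population is the Safety Analysis Set by actual treatment group, with subjects in each baseline category as the denominator;
- the by-visit tables and the abnormal listing stay as they are.

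It would also help to state in 9.5.2 what makes a laboratory value clinically significant for this endpoint, and whether the TEAE tables are meant to carry the investigator-judged part.

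The cost is SAP wording and one extra table per laboratory panel. No new data are needed.
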